9.3 Analysis Populations

The Per Protocol (PP) population will include all subjects and subject data that meets the following criteria specified below:

- 1. Each subject must not have any enrollment violations defined as failure to meet one or more inclusion criteria or meeting one or more exclusion criteria.
- Each subject must receive at least 34 treatments with HemoCare™ in each evaluable study period. All treatments that are initiated with HemoCare™ will be counted regardless of the length of the dialysis session.
- 3. For subjects who meet criteria 1 and 2 above, all adverse events that occur in each Evaluable Period will be counted.

The PP population will be used for analyses of the primary safety endpoint and primary performance endpoint.

The Intent-to-Treat (ITT) population will include all subjects who have used the HemoCare™ at least once during the Assisted Evaluable Period.

Poolability of the data will be examined by assessing the heterogeneity of the primary endpoint results across sites with 5 or more subjects enrolled.

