The Unassisted Home Evaluable Period will conclude after a minimum of 34 treatments (5-10 hours in length). If the subject successfully completes the study, seamless enrollment into the Extension Study (DKPL-00674-001: An Open Label Study to Allow Patients Continuous Use of the HemoCareTM Hemodialysis System for Home Hemodialysis Prior to Market Authorization) is possible, for continued access to the device. If the subject elects not to enroll in the Extension Study, or does not successfully complete the study, the subject will resume HD therapy on another device as prescribed by their regular physician.

4 Objectives and Endpoints

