5.3 Subject Discontinuation/Withdrawal

Subjects may be withdrawn/prematurely discontinued from the study if their participation is discontinued before completion of the Unassisted Evaluation Period. The reason(s) could include:

- 1. Adverse event(s) (AEs)
- Inadequate dialysis
- 3. Protocol violations (i.e., the subject failed to meet protocol entry criteria or did not adhere to the protocol requirements)
- 4. Pregnancy, lactating or not using medically acceptable means of contraception (confirmed by Investigator)
- 5. Lost to follow-up (i.e., subject fails to return for study visits)
- 6. Voluntary withdrawal (i.e., subject's request)

- 7. Termination of the study
- 8. Investigator's discretion
- 9. Renal transplantation
- 10. Switch to Peritoneal Dialysis (PD)
- 11. Subject death
- 12. Other reason (with reason noted on the electronic case report form [eCRF])

The Investigator may terminate a subject's study participation at any time during the study if he/she judges it to be in the subject's best interest. In addition, a subject may discontinue his or her participation at any time during the study. If a subject's participation is discontinued, the reason(s) must be recorded in the source documents and on the eCRFs. If a subject discontinues for any reason, every effort should be made to perform all of the procedures that are scheduled for the last visit. In addition, adverse device effects (ADEs) and all serious adverse events (SAEs), related to study treatment or not, will be followed post-study by the Investigator until the subject is stable or the situation is resolved.

Discontinued subjects will not be replaced unless the targets for enrollment/treatments will not be achieved with the current active group of study subjects. The Investigator or designee should inform their site monitor the moment any subject is discontinued from the study.

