9.4.2 Primary Performance Endpoint

Performance of HemoCareTM Hemodialysis System will be assessed by weekly stdKt/V_{urea} that will be collected every two weeks during each Evaluable Period. A successful weekly stdKt/V_{urea} is defined as a value of at least 2.0. If there is a retest of stdKt/V_{urea} for a

particular week (e.g., a missed or damaged sample) then the retested value will be used for analysis.

During each Evaluable Period, a binary outcome variable will be defined to be 1 if the weekly stdKt/Vurea for a given week meets the success criteria and 0 otherwise. For each subject, this will result in approximately 5 binary outcome values for each period. Each subject will be considered as meeting the primary performance endpoint for that period if all weekly stdKt/Vurea values meet the performance success criterion. A Non-inferiority test will be conducted. The difference in proportion of subjects (P1-P2) meeting the performance criteria in the Unassisted Evaluation Period (P2) and the Assisted Evaluation Period (P1) will be reported with a two-sided 90% CI.

$$H_0: p_1 - p_2 \ge \delta$$

 $H_1: p_1 - p_2 < \delta$

If the upper bound of the Confident interval is less than δ =0.10 then the null Hypothesis is rejected and non-inferiority is demonstrated.

The analysis will be carried out on the PP population. In addition, an analysis using the ITT population and the impact of missing data on the PP analysis will be explored as sensitivity analyses.

Multiple imputation (MI) will be used to assess the sensitivity of missing data on the ITT population. A MI logistic regression model for the efficacy success of each treatment-week will include the following factors: treatment, age, site, and weeks on home dialysis.

A risk difference analysis with continuity correction for independent samples will be performed. Although this will be paired rates, the independent sample analysis will be conducted because it is highly expected not having any failure, at least on the assisted treatment evaluable period.

The same analysis will be conducted using the PP population.

Furthermore, the impact of missing data on the primary analysis, will be explored as sensitivity analysis for both, ITT and PP population.

The evaluation of the primary performance endpoint will be based on the results from the PP population and the ITT population.

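### A subject withdrawn for inadequate dialysis before the 34th Unassisted treatment leaves the per-protocol set used for the performance test, and no rule counts that withdrawal as a failure

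*Combined protocol and SAP*

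**What the plan says.** Section 5.3 covers subjects whose participation is "discontinued before completion of the Unassisted Evaluation Period" and includes "Inadequate dialysis" among the possible reasons. The reason is recorded on the eCRF.

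Section 9.3 sets the entry rule for PP: "Each subject must receive at least 34 treatments with HemoCare™ in each evaluable study period". The count is generous in one respect: "All treatments that are initiated with HemoCare™ will be counted regardless of the length of the dialysis session". ITT is everyone who used the device at least once in the Assisted Evaluable Period.

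Section 9.4.2 defines subject-level success as every weekly stdKt/Vurea in the period being at least 2.0, sampled every two weeks. On the population it says three things:

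- "The analysis will be carried out on the PP population".
- "an analysis using the ITT population and the impact of missing data on the PP analysis will be explored as sensitivity analyses".
- "The evaluation of the primary performance endpoint will be based on the results from the PP population and the ITT population".

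The protocol summary (Analysis Populations) instead makes PP the sensitivity set for both primary endpoints.

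The imputation model in Section 9.4.2 uses treatment, age, site and weeks on home dialysis. Section 9.7 adds single and multiple imputation for both sets, without stating a rule.

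**The concern.** The performance endpoint is dialysis adequacy, and stopping a subject for inadequate dialysis can be the most serious form of failing it. Under the 34-treatment rule, membership of PP can therefore depend on the outcome being tested. A subject with a low value who carries on to 34 treatments counts as a failure. One with the same low value who is withdrawn at, say, Unassisted treatment 12 counts in PP as neither success nor failure.

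The trial is small and expects almost no failures. Section 9.2 works with success rates of 98% to 99% in 30 subjects, so the expected number of failing subjects per period is 30 × 0.01 = 0.3 to 30 × 0.02 = 0.6. One or two subjects may be the whole signal, and the rule that decides whether they are counted can decide the test.

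**Working it through.** **Plan's own figure.** Section 9.2 gives power of 91% at 99% success and 83% at 98%, with 30 subjects per period and a 10% margin. Exact binomial enumeration with equal rates gives 96.4% and 88.2% for an uncorrected Wald 90% interval, and 74.8% and 58.6% with a 1/n continuity correction. No interval method tried gave both stated figures to within 2 points. This is not proof of error: the interval method, the within-subject correlation and the assumed Unassisted shortfall are not given. The point below does not rest on it.

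**Inputs from the plan (Section 9.4.2 unless noted).** Margin 0.10 on P1 − P2 (Assisted minus Unassisted); upper bound of a two-sided 90% interval; independent-sample risk difference with continuity correction; 30 subjects (Section 9.2).

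**Assumptions.** All subjects succeed in the Assisted Period. The number k withdrawn for inadequate dialysis in the Unassisted Period is varied. The form of the correction is not stated, so 1/n, that is (1/n + 1/n)/2, is used, with the uncorrected limit beside it.

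**Formula.** With no Assisted failures and f Unassisted failures among n:

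upper limit = f/n + 1.645 × √[(f/n)(1 − f/n)/n], plus 1/n if corrected.

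**One failure, counted (30/30 v 29/30).** f/n = 0.0333. Standard error = √(0.0333 × 0.9667/30) = 0.0328. Upper limit = 0.0333 + 1.645 × 0.0328 = 0.087; adding 1/30 gives 0.121.

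**Same subject removed (29/29 v 29/29).** Difference and Wald variance are both 0, so the limit is 0, or 1/29 = 0.034 with the correction.

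| k | Counted: corrected | Counted: uncorrected | Removed: corrected | Removed: uncorrected |
|---|---|---|---|---|
| 1 | 12.1% fails | 8.7% passes | 3.4% passes | 0 passes |
| 2 | 17.5% fails | 14.2% fails | 3.6% passes | 0 passes |
| 3 | 22.3% fails | 19.0% fails | 3.7% passes | 0 passes |

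With the correction, one such withdrawal reverses the PP result; without it, two do. The Newcombe interval behaves like the corrected one at k = 1: 13.6% counted, 8.5% removed.

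**Error rate at the margin.** Simulation with an assumed 99% v 89% (true difference exactly 0.10), removing a share of Unassisted failures from both periods:

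| Share of Unassisted failures withdrawn | False non-inferiority, corrected | Uncorrected |
|---|---|---|
| 0 | 3.5% | 14.7% |
| 25% | 8.3% | 28.1% |
| 50% | 18.7% | 48.5% |
| 75% | 44.2% | 73.7% |

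**What ITT does with the same subject.** There are two cases.

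1. A value below 2.0 was recorded in the Unassisted Period before withdrawal. Success needs every value to pass, so the subject is a failure in ITT whatever is imputed later. With 30 in ITT the corrected limit is 12.1%: ITT fails while PP passes at 3.4%.
2. No low value was recorded in that period, because withdrawal fell between two-weekly samples or in Transition Period B. The subject then has only passing Unassisted values, or none. The imputation model contains neither earlier stdKt/Vurea nor reason for withdrawal, so it can fill in success.

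**The case against.** The strongest reply is that PP need not decide the trial. The protocol summary makes PP a sensitivity set, and Section 9.4.2 closes by basing the evaluation on PP and ITT together. A reader might infer from the PP rule that these failures vanish from the analysis and that non-inferiority would then be declared. The documents do not support that: the subject withdrawn at treatment 12 with a recorded low value is a failure in ITT. What remains is that Section 9.4.2 also names PP for the test and calls ITT a sensitivity analysis, with no rule for a PP pass beside an ITT failure.

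Three other strong readings also go too far.

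- A withdrawn subject can never reach 34 treatments. In fact 34 is a minimum ("The Unassisted Home Evaluable Period will conclude after a minimum of 34 treatments"), so someone withdrawn after the 34th Unassisted treatment stays in PP. This is a narrow exception.
- The bias always favours non-inferiority. It does so for lost Unassisted failures; losing an Assisted failure does not favour it.
- Inadequate dialysis in Section 5.3 means stdKt/Vurea below 2.0. The term is not defined there, and withdrawal is permitted rather than required. Section 7.2.6 asks only that the reason for an unmet goal be recorded, and the visit schedules provide for prescription adjustment.

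It is also fair that no withdrawal rate is given, that Section 5.3 allows replacement if targets would be missed (so PP need not shrink to 28 or 29), and that scoring an investigator-recorded reason adds judgement to a laboratory endpoint in an open-label study. These points limit the size of the concern; they do not supply the missing scoring rule.

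**Conclusion.** The concern holds in a limited form. Followed as written, Sections 9.3 and 9.4.2 can remove Unassisted performance failures from the set named for the test, and that loss moves the PP result towards non-inferiority. A single subject is enough under the assumed 1/n correction, and two are enough without it, given 30 subjects and no Assisted failures. ITT is a partial safeguard: it catches recorded low values but not a withdrawal that precedes one. The unresolved roles of PP and ITT leave open which answer would stand.

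The values of k, the withdrawn shares and the form of the correction are assumptions. The documents do not say how many such withdrawals to expect, so this shows how sensitive the test is and does not predict the bias.

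**What to change.** Amend Sections 9.3 and 9.4.2, and carry the change into the SAP, before results are seen:

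1. A subject with any recorded stdKt/Vurea below 2.0 in an Evaluable Period, or whose recorded reason for discontinuation during that period is inadequate dialysis, is a performance failure for that period. The subject stays in the performance analysis set, PP and ITT, whatever the number of treatments.
2. Pre-specify how discontinuation for this reason in Transition Period B is handled. The endpoint covers Evaluable Periods only, so assigning it to the Unassisted Period is debatable; a sensitivity analysis counting it as an Unassisted failure is one option.
3. Reconcile the protocol summary with Section 9.4.2 on the roles of PP and ITT, and require both to meet the margin.

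The cost is a few sentences and no new data, since the reason is already on the eCRF. Withdrawal rules and clinical care are untouched. The downside is that the result may look slightly less favourable and the endpoint takes in an investigator-recorded reason.

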9.4 Primary Endpoints

9.4.1 Primary Safety Endpoint

The primary safety analysis will be to compare the Unassisted Home Evaluable Period AE rate per 100 HemoCareTM Hemodialysis System treatments against the Assisted Evaluable Period AE rate per 100 HemoCareTM Hemodialysis System treatments. A two-sided 90%

CI will be generated for the rate ratio $(\lambda 2/\lambda 1)$ comparing the relative difference in AEs for the two scenarios using a negative binomial regression model. The analysis will be carried out on the ITT population. The response variable is the total number of AEs. The model will include an indicator variable that is equal to one if treatment is "Assisted Evaluable Period" and zero otherwise. In addition, the log of the number of treatments will be included as an offset variable in the model and a subject specific random effect for treatment period will be included with covariance structure specified as "unstructured."

Let $\lambda_i = \frac{n_{aei}}{N_{txi}}$ be the rate of adverse event during treatment $i = \{a \text{ for assisted treatment} \}$ $\{a \text{ for unassisted trreatment} \}$

Where:

 $n_{aei} = Number \ of \ adverse \ event \ during \ treatment \ i, and \ N_{txi} = Number \ of \ treatment \ type \ i$

Given a non-inferiority margin δ ,

$$H_0: \frac{\lambda_u}{\lambda_a} > 1 + \delta$$
 $H_1: \frac{\lambda_u}{\lambda_a} \le 1 + \delta$

The Negative Binomial distribution will be used as a link function with the log transformation will be used to estimate the ratio and it's Confidence Interval. The logarithm of the Number of treatment for each treatment modality will be included as an offset term to account for any potential unpredicted unbalance between the two modalities sample sizes. If the Negative Binomial model fail to converge, the Poisson distribution with Scale =Dispersion will be adjusted.

Let UCI be upper boundary of the $\frac{\lambda_u}{\lambda_a}$ ratio confidence interval. H_0 is rejected if UCI $\leq 1 + \delta$ resulting in accepting H_1 and concluding Unassisted treatment are not inferior than assisted treatment.

The same analysis will be conducted using the PP population.

The evaluation of the primary safety endpoint will be based on the results from the ITT population and the PP population.

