	Upon successful completion of training, the subjects will enter Transition Period A (1 to 2 weeks) which may occur at the study site or be transitioned to the home setting. The subjects will receive training and extended duration HD (5-10 hours per treatment) at least 3 times every seven days.
	This will be followed by the Assisted Evaluable Period during which the subjects will receive training and a minimum of 34 HD treatments (5-10 hours per treatment) with treatments prescribed to occur every other day, preferably in a home setting, with HemoCare TM Hemodialysis System. Alternatively, the treatment can also be administered at the study site based on clinician's judgment and/or subject's preference. The treatment will be administered by a Medical Professional during the Assisted Evaluable Period.

After successful completion of the Assisted Evaluable Period, subjects will begin Transition Period B (1 to 2 weeks) and can be extended if additional training is required in the Home setting. The treatment during this Period could be performed in the absence of a Medical Professional, but they will visit the subjects' home if need be.

This will be followed by the Unassisted Home Evaluable Period where subjects will receive a minimum of 34 HD treatments (5-10 hours per treatment) with treatments prescribed to occur every other day with HemoCareTM Hemodialysis System.

[figure not shown]
Investigators will ensure the subjects' prescriptions achieve dialysis adequacy targets per local standard of care. The Investigator will evaluate any prescription changes during Evaluable Periods and they will be documented in the HemoCareTM Connectivity Platform. Trial subjects will be encouraged to remain in the same prescription frequency and duration in Assisted Evaluable Period and Unassisted Home Evaluable Period. Deviations in treatment frequency and duration can occur, on a treatment-by-treatment basis, within a range approved by the Investigator as stated in their care plan. AEs and dialysis system performance parameters will be collected throughout the study, but only AEs collected during the Evaluable Periods will be used for the comparison of safety between the two Evaluable Periods (Assisted and Unassisted).

Inclusion Criteria:

All of the following criteria must be met for the subject to be eligible for participation. The study will enroll subjects who:

- 1. Have been diagnosed with ESRD and are \geq 18 years of age.

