2 INTRODUCTION

2.1 Study Rationale:

According to the 2017 United States (US) Renal Annual Data Report at the end of 2015, nearly 700,000 dialysis and transplant patients were receiving treatment for end-stage renal disease (ESRD). At the end of 2015, 85% of all prevalent cases receiving hemodialysis (HD) were receiving the same at an in-center setting. Overall survival probabilities for all dialysis patients remain poor. In the same US Renal Annual Data Report, the 5-year survival rate for HD patients was 42 %. Furthermore, on average, HD patients are hospitalized 1.7 times per year with an average length of stay being 11.4 days. In 2015, the overall costs to treat 434, 914 ESRD Medicare patients (<1% of all Medicare beneficiaries) were \$33.9 Billion, accounting for 7 % of all Medicare spending.¹

An expanding body of scientific literature indicates that clinical outcomes of suitable HD patients can be improved with HD treatments that are longer and/or more frequent in duration than conventional HD. A typical treatment schedule for the vast majority of HD patients in the US is 3 treatments per week, with each treatment lasting no more than 4 hours. In contrast, extended duration therapies can be 5 to 10 hours in duration and 3 to 6 times per week. Compared to conventional HD, these long dialysis therapies enable lower ultrafiltration (UF) rates and provide greater removal of middle molecules such as β2 microglobulin, higher phosphate clearances, and less fluctuation in electrolytes and extracellular fluids.² Compared to patients receiving conventional HD, patients treated with frequent nocturnal HD experience improved blood pressure control^{3,4}, improved serum phosphorus control^{3,4}, regression of left ventricular mass³, and improved quality of life.³In an observational study of 177 patients treated with home frequent nocturnal HD, the 5 year survival rate was 85%, similar to the survival rate in a matched cadaveric renal transplant cohort.⁵

Short daily HD offers many of the same benefits as frequent nocturnal HD, but the latter is associated with greater uremic toxin clearances and perhaps greater improvements in cardiovascular health.²⁻⁴ The risks associated with both short daily HD and frequent nocturnal HD are similar in many ways. More frequent use of the vascular access may be associated with greater risks of vascular access failure or infection. Increased blood and iron loss may occur with more frequent HD.

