The process for the collection of subject reported events will be the same for both Evaluable Treatment periods. Raw events will be collected through the Weekly Assessments, as well as routine medical record review and standard of care communications with the subject and/or care partner.

All AEs and SAEs, regardless of relatedness, should be recorded.

Additionally, any AE voluntarily reported by the subject should be recorded and verified by the Investigator or designee on the appropriate source documents and eCRF pages.

The outcome/resolution of all AEs and SAEs will be determined by the Investigator and documented on the AE eCRF. Investigators will be instructed to follow all AEs/SAEs as follows: Unrelated AEs will be followed until resolution or until the end of the study whichever occurs first. Adverse device effects (related AEs) and all SAEs (related or not) will be followed until resolution or stable, including following the subject after the end of the study if necessary. The outcome categories that can be chosen on the eCRF by the Investigator include: Fatal, not recovered/not resolved (this outcome is reached for AEs which are ongoing when the subject's end of study is due to death related to another AE), Recovering/Resolving (this outcome is reached for AEs which are ongoing at the subject's end of study), Recovered/Resolved with Sequelae (if there are some residual effects caused by the event), Recovered/Resolved, and Unknown.

All SAEs regardless of their relationship to the study product will be submitted to Sponsor or designee by the Investigator or designee within 24 hours of becoming aware of the event. If an investigator becomes aware after study completion of an SAE that occurred in a subject during their participation in the study, the SAE must be reported on the SAE Form within 24 hours after awareness. Serious adverse events occurring within 30 days of study completion (per subject) will also be reported.

An AE can result from the use of the study product in accordance with the protocol, as well as from an accidental or intentional misuse of the study product or any other treatment error such as unintentional administration or use of another product during the course of the study.

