8.2 Adverse Event Reporting

8.2.1 Reporting Adverse Events to Sponsor/Designee

During the course of the study, the Investigator or designee will routinely monitor each subject for the occurrence of any AE/ADE. If an AE/ADE occurs, the Investigator or designee will complete the AE eCRF which includes the following:

- Description of the event
- Start and stop date of the event
- Timing of the event (prior to first study treatment, during treatment set-up, during treatment, within 4 hours after treatment ends, > 4 hours after treatment ends)

[figure not shown]

- Seriousness of the event (yes, no) (assessed by PI or Sub-I)
- Severity of the event (mild, moderate, or severe) (assessed by PI or Sub-I)
- Causality of the event (related to treatment and/or related to the device) (assessed by PI or Sub-I)
- Action taken
- Outcome of the event (fatal, not recovered/not resolved, recovered/resolved with sequelae, recovered/resolved, and unknown)

All SAEs must be reported to the Sponsor/designee within 24 hours of the Investigator or designee becoming aware of its occurrence. The informed site team member should also contact their site monitor by phone or email to notify him/her of the event. This requirement is irrespective of whether the AE is thought to be possibly related to the study product or not. Expedited Reporting of Serious Adverse Events and Suspected Unexpected Serious Adverse Reaction (SUSAR). Sponsor/designee will assess each SAE reported by the Investigator to determine if the SAE qualifies as an expedited report according to FDA criteria. Sponsor/designee will report to FDA according to the applicable time requirements.

Per regulations, when an Unexpected Adverse Device Effect (UADE) or SUSAR occurs Investigators will receive a letter from Sponsor/designee describing the UADE/SUSAR. The Investigator should file this letter within their Investigator Study Binder. Additionally, the expedited report letter should be submitted by the Investigator to their IRB/REB, as appropriate per FDA regulations.

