9.2 Determination of Sample Size

The goal is to have at least 1000 HemoCare™ treatments in both Evaluable Periods, in agreement with the FDA, to make a *clinical determination* of the safety of HemoCare™ based on the rate and type (i.e., device related) of AEs documented. To achieve this goal, at least 30 subjects will enter the Assisted Evaluable Period. No more than 25% of the total study subjects who complete the study may be enrolled at one site. Assuming each Evaluable Period is 3.5 treatments per week (one treatment every other night), each patient is expected to contribute 34 treatments to each Evaluable Period and 68 evaluable treatments to the study.

Based upon the number of treatments and the expected rate of adverse events, the current study design is under-powered to detect a clinically meaningful (less than 10%) non-inferiority margin for the Unassisted Evaluable Period.

For the primary performance endpoint, 'success' is defined as a subject who has all stdKt/Vurea measures in an evaluable period greater than or equal to 2.0. Several sets of simulation samples were generated (2,000 samples per set) assuming a rate of success between 95% and 99.5% for the Assisted Evaluable Period treatments paired with some fewer successes for the Unassisted Evaluable Period treatments. The success rate of the 2 periods were compared and the CI interval for the differences were calculated. With 30 subjects in each Evaluable Period, a margin of 10% will provide 91% power to declare non-inferiority if the actual success rate is 99% and 83% power if the actual success rate is 98%.

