9.5 Secondary Endpoints

 Adverse events will be mapped to a primary MedDRA System Organ Class (SOC) and Preferred Term (PT). Anticipated AEs and SAEs and unanticipated AEs and SAEs will be summarized during each Evaluable Period by SOC and PT. In addition, all devicerelated AEs and SAEs will be summarized during each Evaluable Period by SOC and PT.

An overview of the total number of AEs and SAEs (anticipated, unanticipated, and device-related) during each Evaluable Period will be provided. In addition, for each Evaluable Period an overview will be provided of the total number of subjects having at least 1:

- Anticipated AE
- Anticipated SAE
- Unanticipated AE
- Unanticipated SAE
- Device-related AE
- Device-related SAE

The proportion of subjects having at least one AE within each of these six AE subgroups will be compared between Evaluable Periods with exact McNemar's tests. For each of these six AE subgroups the hypotheses will be:

$$H_0: P_u = P_a$$

 $H_a: P_u \neq P_a$

Where P_u = Proportion of subject having at least 1 event during unassisted treatments and P_a is the proportion of subjects having at least 1 event during the Assisted treatments.

Identifying the number of subjects who had at least 1 event during assisted treatment and no event during unassisted treatment as n_{12} , and subjects who have no event during assisted treatment and at least 1 event during unassisted treatment as n_{21} , the indicator

$$Q = \frac{(n_{12} - n_{21})^2}{(n_{12} + n_{21})}$$
 will be compared to x^2 with 1 Degree of Freedom if

$$(n_{12} + n_{21}) > 20$$
. Otherwise the correction $Q = \frac{(|n_{12} - n_{21}| - 1)^2}{(n_{12} + n_{21})}$ will

be used. The Null Hypothesis will be rejected if the P-value for the x^2 is less than 0.10.

No multiplicity adjustment will be done for these secondary endpoints.

Furthermore, the proportion of subjects having AEs within each of these six AE subgroups will be summarized by SOC, PT and severity (mild, moderate or severe) during each Evaluable Period for the most severe rating of each AE per subject.

 The incidence of decreased serum phosphorus defined as at least 1 post-dialysis serum phosphorus level < 2.2 mg/dL, the incidence of elevated serum phosphorous defined as a least 1 post-dialysis serum phosphorus level > 5.5 mg/dL, will each be compared between Evaluable Periods with exact McNemar's tests.

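### The primary safety ratio counts all AEs whatever their relation to device or treatment, and no rate ratio with an interval is specified for device-related, treatment-related or peri-treatment AEs

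*Combined protocol and SAP*

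**What the plan says.** Section 9.4.1 makes the AE rate per 100 treatments the primary safety measure and models it with the log number of treatments as offset. On the outcome it says: "The response variable is the total number of AEs". Section 8 sets the scope of what is recorded: "All AEs and SAEs, regardless of relatedness, should be recorded". The Protocol Summary limits the comparison by study period: "only AEs collected during the Evaluable Periods will be used for the comparison of safety between the two Evaluable Periods".

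Section 9.2 says that the clinical determination of safety will be made "based on the rate and type (i.e., device related) of AEs documented".

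The AE form (Section 8.2.1) has separate entries for relation to treatment and relation to the device. It also has a timing entry whose categories include "during treatment set-up, during treatment, within 4 hours after treatment ends".

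Device-related events are covered among the secondary endpoints. Section 4.2.2 lists their number per period. Section 9.5 says that "all devicerelated AEs and SAEs will be summarized during each Evaluable Period by SOC and PT", adds a summary by severity, and compares the proportion of subjects with at least one such event by McNemar tests at P < 0.10. Section 9.8 refers further AE analyses to the SAP.

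**The concern.** The trial asks what changes when the Medical Professional no longer runs the treatment. The events most likely to respond are those tied to set-up, vascular access and the treatment itself. Intercurrent illness should be much the same in both periods. Adding it to numerator and denominator alike moves the ratio toward 1, and in a non-inferiority comparison that is the favourable direction.

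The planned device-related comparison does not make up for this. A subject with one event and a subject with five count the same, and exposure does not enter. Each period is a minimum of 34 treatments and may be extended (Section 9.7.1), so exposure can differ between periods. For treatment-related AEs, and for timing relative to treatment, the documents describe no analysis, although the fields are on the form. At stake is whether the data put before the clinical determination show a rise confined to these events at its true size and with a measure of its uncertainty.

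**Working it through.** **The plan's own figure.** 30 subjects × 34 treatments = 1,020 treatments per period, which meets the Section 9.2 goal of at least 1,000 (read here as per period). With 29 subjects it would be 29 × 34 = 986. The documents state no expected AE rate, no related share and no value for the safety margin δ. The inputs below marked as assumed are therefore ranges, not estimates.

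**Dilution.** Let f be the device-related share of Assisted AEs (assumed), R the true Unassisted/Assisted ratio for those AEs (assumed), and let all other AEs have equal rates in the two periods. Then

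all-AE ratio = (1 − f) + f × R.

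| f | R = 2 | R = 3 |
|---|---|---|
| 5% | 1.05 | 1.10 |
| 10% | 1.10 | 1.20 |
| 20% | 1.20 | 1.40 |
| 50% | 1.50 | 2.00 |

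**One worked case.** Assume 10 AEs per 100 Assisted treatments, f = 10%, R = 2 and 1,020 treatments per period. The SE of the log ratio is √(1/E_a + 1/E_u), where E_a and E_u are the expected events. This is Poisson with no overdispersion, so it is optimistic.

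- All AEs: 102 against 112.2 events. The ratio is 1.10, SE = 0.137, 90% CI 0.88 to 1.38. The chance that the lower limit exceeds 1 is about 17%.
- Device-related AEs: 10.2 against 20.4 events. The ratio is 2.0, SE = 0.383, 90% CI 1.06 to 3.76. The chance that the lower limit exceeds 1 is Φ(0.693/0.383 − 1.645), about 56%.

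The smaller set gives a wider interval but still carries more of the signal. For comparison, with no true difference and 10 AEs per 100 treatments, the all-AE upper limit would be about 1.26. An all-AE result of 1.10 (0.88 to 1.38) would not stand out.

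**The planned McNemar test against a rate ratio.** The McNemar figures are simulated: 30 subjects, 34 treatments per period, Poisson counts independent between periods, P < 0.10 in the direction of more affected subjects in the Unassisted period. The exact and the continuity-corrected forms gave practically the same results. The rate-ratio column is the formula above. The true device-related rate doubles in each row.

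| Assisted device-related AEs per 100 | Expected events | McNemar power | Rate ratio, lower 90% limit > 1 |
|---|---|---|---|
| 0.5 | 5.1 vs 10.2 | 22% | 36% |
| 1 | 10.2 vs 20.4 | 39% | 56% |
| 2 | 20.4 vs 40.8 | 55% | 82% |
| 4 | 40.8 vs 81.6 | 50% | 98% |
| 8 | 81.6 vs 163.2 | 4% | over 99% |

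The last row shows why the test fails at high rates. At 8 per 100 the mean is 8 × 0.34 = 2.72 events per subject, so 1 − e^(−2.72) = 93% of subjects have at least one event in the Assisted period. After doubling, the figure is 1 − e^(−5.44) = 99.6%. Almost no discordant pairs remain. Overdispersion would lower the rate-ratio figures.

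**The case against.** Much can be said for the plan.

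- Section 9.2 can be read as asking for an overall rate plus a breakdown by type, because its parenthesis qualifies type. Sections 9.4.1 and 9.5 supply both. This stands: a reader might infer that Section 9.2 promises a device-related rate that is then never estimated, and the text does not say so. A crude rate also follows from the planned device-related count and the number of treatments.
- A reader might infer that a rise in device-related events would be hidden. It would not be. It is diluted in the primary ratio, but the events are still counted, tabulated and tested by period.
- A reader might infer that timing is ignored altogether. Only Evaluable Period AEs enter the comparison. What goes unused is timing relative to a treatment.
- Counting all AEs avoids reliance on causality and timing codes, which are open-label judgements. Capture may also differ. Section 7.1.4 has the Medical Professional giving the treatment, the subject or the care partner report AEs at each treatment, while Section 7.1.7 relies on the weekly call. Section 8 says that the process for subject-reported events is the same in both periods, but that does not remove the difference in who is present. This is a good reason to keep the total as primary.
- δ has no stated value, and Section 9.2 calls the design under-powered for a clinically meaningful margin. The documents therefore give no numerical safety threshold that dilution would help the device to pass.
- Section 9.8 refers further AE analyses to the SAP, and the numbering goes from 9.5 to 9.7. Absence can be stated only for the text available.

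What remains is that no rate ratio with an interval is specified for the events most likely to respond, and the stated substitute is weak.

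**Conclusion.** The point holds as a gap in supportive analysis, not as a fault in the choice of primary endpoint. The all-AE ratio understates a rise confined to device-related events: a doubling appears as 1.05 to 1.20 when those events are 5% to 20% of Assisted AEs. The McNemar comparison has about 22% to 55% power for a doubling at 0.5 to 4 events per 100 treatments and about 4% at 8 per 100. A rate ratio has about 36% to 98%, and over 99%, on the same footing. The gap is wider for treatment-related AEs, which get no summary by causality. The anticipated-AE group is only a proxy for them.

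These sizes rest on assumed shares, rates and ratios, on equal rates of other AEs in the two periods, and on Poisson variation. The documents give no figure for the background share. A reader might be tempted to take one from Section 2.1, where "HD patients are hospitalized 1.7 times per year". That is an all-cause average which the protocol does not describe as unrelated to dialysis, and without a total AE rate it cannot be turned into a share.

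**What to change.** Keep the total-AE ratio in Section 9.4.1 as primary. Pre-specify, as supportive analyses, the AE rate per 100 treatments in each period and the Unassisted/Assisted ratio with 90% CI, from the same model with its Poisson fallback, for:

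1. device-related AEs;
2. treatment-related AEs;
3. AEs during set-up, during treatment, or within 4 hours after it ends.

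For the first two, state that the grades related and possibly related both count as related. Section 8.1.1 defines four grades, while Section 8.2.1 lists only relation to treatment and/or device. Report the three ratios beside the total for the Section 9.2 clinical determination. If the SAP already contains them, a citation in Section 9.4.1 is enough.

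The cost is wording and three more runs of a planned model on fields already on the form, with no new data or subjects. Event numbers will be smaller, intervals wider, and the fallback more likely to be needed. Because causality and timing codes are open-label and may be captured differently in the two periods, the text should say that these ratios support the primary analysis and do not replace it. They should be fixed in advance, since subsets chosen after seeing open-label data would carry little weight.
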